- 3) Record review for appropriate diagnosis and stage of disease or confirmation of diagnosis by internal pathology review of initial or subsequent biopsy or other pathologic material at UWMC
- 4) Baseline pulse oximetry and documentation of O2 saturation on room air
- 5) Baseline 12-lead EKG
- 6) Patients 60 years or older: Echocardiogram or MUGA scan within 60 days of enrollment.
- 7) Baseline imaging with RECIST read (generally CT chest/abdomen/pelvis (and if present affected extremity), MRI brain if history of brain metastasis or neurologic symptoms concerning for brain metastasis, CT neck if prior cervical adenopathy, MRI or PET may be substituted as clinical judgement dictates). Imaging must be repeated if not within 45 days prior to first infusion of FH-MagIC TCR-T

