**Research samples:**

- 1) PBMC Baseline Samples: A 60 ml blood sample (in EDTA [lavender top] tube) for research should be sent to the Specimen Processing/Research Cell Bank lab at the Fred Hutch for PBMC isolation and cryopreservation. These cells will be used as PBMC baseline samples for comparison to post-treatment samples for all cellular correlative tests, including T cell persistence and immunophenotype by flow cytometry or Q-PCR or TCR-β deep sequencing (e.g., with Adaptive Biotechnologies) assays, assessment of anti-transgene and anti-tumor immune responses. These tests are all optional and may be performed depending on tumor response and T cell persistence.
- 2) Baseline serum: A 20 ml blood sample (serum separator tube) should be sent to the Specimen Processing/Research Cell Bank lab at the Fred Hutch to be used as serum baseline to assess anti-transgene and anti-tumor immune responses. These tests may be performed depending on tumor response and T cell persistence.
- 3) Other biopsy or sample: If biopsy or sampling of tissues (i.e., CSF, pleural fluid, etc.) is performed for clinical indications, then additional tissue may be obtained during the same procedure and sent to the Specimen Processing/Research Cell Bank Lab at the Fred Hutch for research studies. Please discuss the planned procedure with the study PI.
- 4) RCL Testing: A 10 ml (EDTA/lavender top) blood sample should be collected as baseline for RCL testing and sent to the Specimen Processing Lab/ Research Cell Bank Lab at the Fred Hutch.
- 5) Research RECIST 1.1 read of baseline scans.
- 6) Biopsy samples: Enrollment (after eligibility and prior to bridging chemo if given and LD) research biopsy samples defined as a core needle (6 needle passes) or punch biopsy (1 x 6 mm or 2 x 4 mm) will be obtained.

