#### **10.4 Evaluations within 5 days before LD if receiving (if no LD planned, then within 2 days before cell infusion)**

- 1) Interval history and physical exam and ECOG performance status
- 2) Blood draw for laboratory studies:
  - a. CBC, differential, platelet count
  - b. Renal/Hepatic Function Panel
  - c. Magnesium and Lactate Dehydrogenase (LDH)
  - d. Research Labs:
    - i. A 30 ml blood sample (in EDTA [lavender top] tube) for research should be sent to the Specimen Processing/Research Cell Bank lab
    - ii. A 10 ml blood sample (serum separator tube) should be sent to the Specimen Processing/Research Cell Bank lab
- 3) In order to be eligible for LD/TCR infusion, the patient must meet the following pre-infusion criteria:
  - Continue to meet all inclusion/exclusion criteria
    - All assessments do not need to be repeated at this timepoint, but if there are any incidental findings between screening assessments and this timepoint that would make the patient ineligible, they will be excluded from moving forward with LD/cell infusion
  - No disease complications from bridging therapy or related to the patient's underlying disease that, in the opinion of the investigator, would make it unsafe to proceed with LD chemotherapy or TCR infusion.
  - Adequate respiratory function with oxygen saturation  $\geq 94\%$  on room air and no dyspnea at rest.
  - No new cardiac issues, including CHF, MI, arrhythmias, or stroke.
  - No evidence of an active infection (e.g., temperature  $\geq 38.3^{\circ}\text{C}$ , positive blood cultures, requirement for antibiotics) within 14 days before LD chemotherapy.

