## **10.7 Response Assessment**

Participants will have evaluation of tumor burden at baseline (physical exam with tumor measurements, cross-sectional imaging as detailed above, RECIST 1.1 and imRECIST reads of cross-sectional imaging), at approximately 12 weeks after T cell infusion, and then at discretion of treating oncologist (suggested frequency every 3-6 months). *Note:* in patients who receive a second T-cell infusion, repeat baseline imaging should be performed (within 30 days before starting LD chemotherapy or T cell infusion if no LD chemotherapy is given) and again at timepoints outlined above. These assessments have a window of +/- 7 calendar days. Imaging should also be performed if suspicion of progression. Imaging will be performed on a clinical basis with RECIST 1.1/imRECIST reads on a research basis.

Participants will have research biopsy of tumor at baseline, at approximately 12 weeks after first T cell infusion, and if clinically suspected to have progression. Additional research biopsies are planned at 2 weeks post T cell infusion and at 12 weeks after second T cell infusion, and additional research tissue may be requested from clinical biopsies.

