d ECHO required if patients  $\geq$ 60 years of age within 60 days of enrollment.

e Diagnostic CT/PET scan to include neck, chest, abdomen and pelvis, as clinically indicated by disease.

f In patient who receive lymphodepleting chemotherapy, quantitative IgG to be measured approximately monthly until levels are normal without IVIG replacement. If levels are still abnormal at the end of follow-up, IgG should continue to be assessed by the treating physician.

g Pregnancy test within 72 hours of cell infusion

RG1007463  
IR10420

- b If history of brain metastasis or neurologic symptoms
- i Repeat imaging if not within 45 days of infusion day

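### The RECIST baseline for the first infusion can be a scan taken before bridging chemotherapy, so tumor change from bridging can enter the response count

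*Combined protocol and SAP*

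**What the plan says.** Item 7 of the baseline evaluations (before section 10.3) calls for imaging with a RECIST read and sets an age limit: "Imaging must be repeated if not within 45 days prior to first infusion of FH-MagIC TCR-T". Appendix A places the CT/PET scan in the pretreatment column, with no scan in the LD column, and footnote i gives the same limit: "Repeat imaging if not within 45 days of infusion day".

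Bridging appears in two places. Item 6 of the research samples list times a biopsy against it: "Enrollment (after eligibility and prior to bridging chemo if given and LD) research biopsy samples". Section 10.4 makes it part of the check before LD: "No disease complications from bridging therapy or related to the patient's underlying disease" that would make it unsafe to go on. Neither section 10.4 (before LD) nor section 10.5 (day of infusion) lists imaging.

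The second infusion has its own rule in section 10.7: "repeat baseline imaging should be performed (within 30 days before starting LD chemotherapy or T cell infusion if no LD chemotherapy is given"). Section 10.8 adds a washout for therapy given for progression between the two infusions.

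The scheduled post-treatment assessment is "at approximately 12 weeks after T cell infusion" (section 10.7). Section 12.3.1 defines response as a best overall RECIST 1.1 response of CR or PR. Section 12.3.2 tests this against a fixed 5% and concludes potential efficacy if three or more patients respond, quoting a probability of .04 for three or more of 16 at a true rate of 5%.

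**The concern.** The trigger for a new scan is its age. Treatment given after the scan is not a trigger. A patient scanned on day -40, then bridged, lymphodepleted and infused on day 0 would comply with item 7 and footnote i and would keep the pre-bridging scan as the RECIST reference. Any change in the target lesions between scan and infusion is then part of the measured response.

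This can mislead in both directions. Shrinkage on bridging brings a patient closer to PR before any T cells are given. Growth before infusion makes a real T-cell effect harder to register. With a threshold of three responders, a few misattributed patients could change the conclusion. The gap cannot be repaired later, because a post-bridging, pre-infusion scan cannot be obtained after the infusion.

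**Working it through.** **Inputs from the documents.** N = 16, success at 3 or more responses, null rate 5% (12.3.2); response = CR or PR by RECIST 1.1 (12.3.1); 45-day limit (item 7, footnote i).

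**Inputs assumed.** Share bridged *f* and chance *r* that bridging alone produces a PR against the pre-bridging scan; the documents give neither. The PR threshold is the usual RECIST 1.1 fall of 30% in the target sum, which the documents invoke by name without restating.

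**Step 1: the plan's own figure.** P(X ≥ 3 | 16, 0.05) = 1 − (0.95^16 + 16 × 0.05 × 0.95^15 + 120 × 0.05² × 0.95^14) = 0.0429. The stated .04 is reproduced.

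**Step 2: what a pre-bridging baseline does to one patient.** If the target sum is multiplied by *c* between scan and infusion, the further shrinkage needed for PR is 1 − 0.70/*c*.

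| Change before infusion | *c* | Further shrinkage needed |
|---|---|---|
| none | 1.00 | 30% |
| −10% | 0.90 | 22.2% |
| −20% | 0.80 | 12.5% |
| −30% | 0.70 | 0% |
| +25% | 1.25 | 44% |

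**Step 3: effect on the success rule.** Two models bracket what the 5% might mean.

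- Additive: the T cells give 5% and bridging adds to it independently. Apparent rate p = 1 − 0.95 × (1 − *f* × *r*).
- Inert T cells: every apparent response comes from bridging. Apparent rate p = *f* × *r*.

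| *f* / *r* | Additive p | P(≥3 of 16) | Inert p | P(≥3 of 16) |
|---|---|---|---|---|
| 25% / 10% | 7.4% | 0.109 | 2.5% | 0.007 |
| 50% / 10% | 9.75% | 0.200 | 5% | 0.043 |
| 50% / 20% | 14.5% | 0.416 | 10% | 0.211 |

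Neither model allows for bridging responses that are lost before the 12-week scan, or for growth before infusion, which works the other way.

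**The case against.** Five arguments weigh against a stronger reading.

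First, a reader might infer that the protocol has no post-bridging imaging rule at all. The documents do not support that: the text reviewed begins at item 3 of the baseline evaluations, and the section that would set out bridging and any restaging is not in it. The point stands only for the text reviewed.

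Second, a reader might infer that nothing re-checks disease status after bridging. Section 10.4 says assessments need not all be repeated, but it requires patients to go on meeting the entry criteria and excludes those with incidental findings that make them ineligible. Eligibility is therefore still checked, although no scan is listed.

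Third, the 45-day limit may often force a later scan. Appendix A carries a window of 30 days before leukapheresis, although the table is broken and the column it belongs to is unclear. Taken at face value, a scan at that limit expires unless infusion follows within 45 − 30 = 15 days. This stands as a reason why the problem may be uncommon. It does not close the gap, because a renewed scan need not fall after bridging. The time from leukapheresis to infusion is not given.

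Fourth, section 12.3.2 calls responses to alternative therapies in this population rare and sets 5%. Bridging response rates of 10% to 20% are two to four times that benchmark, and a bridging response would usually have to last to about 12 weeks to count. This stands: the additive results are not estimates of what will happen.

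Fifth, one could say that a single bridging response raises the false-success probability to 0.17, the chance of at least 2 responses among the other 15 at 5%. That figure assumes the harmful event has already happened, so it is not an operating characteristic of the design.

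**Conclusion.** The gap is real in the text reviewed: a compliant first-infusion baseline can predate bridging, and any resulting tumor change counts toward best overall response and the three-responder rule. Item 6 of the research samples list times the enrollment biopsy against bridging; the imaging rule has no such link.

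A reader might conclude that bridging shrinkage will be credited to the T cells and that the error rate is therefore inflated. The documents do not show that. The share bridged, the bridging response rate and the timing are all unknown, and growth before infusion biases the other way, so neither the size nor the net direction of the bias is known. Under the assumptions shown, the false-success probability ranges from 0.007 to 0.42 against 0.043, and in two of the three inert-T-cell scenarios it does not rise above 0.043. Even there, a declared success could not be attributed to the T cells.

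This is a should-fix. The decision at stake is whether the regimen merits further study in a trial of 15-18 patients, and the remedy is small.

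**What to change.** Add to item 7 and to Appendix A footnote i: *or if any bridging therapy was given after the scan; the RECIST 1.1/imRECIST baseline is the last scan after bridging ends and before LD, or before T cell infusion if no LD is given.* This is in line with section 10.7, which ties the second-infusion baseline to LD, or to infusion where there is no LD.

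Report responses by bridging status. If a bridged patient has no post-bridging scan, repeat the 12.3.2 decision as a sensitivity analysis that excludes that patient's response. Automatic non-responder status would be too harsh, since it would discard a genuine response even where bridging had done nothing. The plan should also say how it counts a bridged patient whose new baseline shows no trackable lesion, because 12.3.1 requires one.

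The cost is one clause in two places and a re-timed, or occasionally repeated, clinical scan in bridged patients only. The sample size does not change, and nothing here bears on whether or how bridging is given. If an earlier section of the protocol already sets a post-bridging imaging rule, item 7 and footnote i should be reconciled with it.

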**Research samples:**

- 1) PBMC Baseline Samples: A 60 ml blood sample (in EDTA [lavender top] tube) for research should be sent to the Specimen Processing/Research Cell Bank lab at the Fred Hutch for PBMC isolation and cryopreservation. These cells will be used as PBMC baseline samples for comparison to post-treatment samples for all cellular correlative tests, including T cell persistence and immunophenotype by flow cytometry or Q-PCR or TCR-β deep sequencing (e.g., with Adaptive Biotechnologies) assays, assessment of anti-transgene and anti-tumor immune responses. These tests are all optional and may be performed depending on tumor response and T cell persistence.
- 2) Baseline serum: A 20 ml blood sample (serum separator tube) should be sent to the Specimen Processing/Research Cell Bank lab at the Fred Hutch to be used as serum baseline to assess anti-transgene and anti-tumor immune responses. These tests may be performed depending on tumor response and T cell persistence.
- 3) Other biopsy or sample: If biopsy or sampling of tissues (i.e., CSF, pleural fluid, etc.) is performed for clinical indications, then additional tissue may be obtained during the same procedure and sent to the Specimen Processing/Research Cell Bank Lab at the Fred Hutch for research studies. Please discuss the planned procedure with the study PI.
- 4) RCL Testing: A 10 ml (EDTA/lavender top) blood sample should be collected as baseline for RCL testing and sent to the Specimen Processing Lab/ Research Cell Bank Lab at the Fred Hutch.
- 5) Research RECIST 1.1 read of baseline scans.
- 6) Biopsy samples: Enrollment (after eligibility and prior to bridging chemo if given and LD) research biopsy samples defined as a core needle (6 needle passes) or punch biopsy (1 x 6 mm or 2 x 4 mm) will be obtained.

**10.3 Evaluations prior to leukapheresis**

Treatment consent signed and eligibility confirmation must be completed prior to leukapheresis start.

#### **10.4 Evaluations within 5 days before LD if receiving (if no LD planned, then within 2 days before cell infusion)**

- 1) Interval history and physical exam and ECOG performance status
- 2) Blood draw for laboratory studies:
  - a. CBC, differential, platelet count
  - b. Renal/Hepatic Function Panel
  - c. Magnesium and Lactate Dehydrogenase (LDH)
  - d. Research Labs:
    - i. A 30 ml blood sample (in EDTA [lavender top] tube) for research should be sent to the Specimen Processing/Research Cell Bank lab
    - ii. A 10 ml blood sample (serum separator tube) should be sent to the Specimen Processing/Research Cell Bank lab
- 3) In order to be eligible for LD/TCR infusion, the patient must meet the following pre-infusion criteria:
  - Continue to meet all inclusion/exclusion criteria
    - All assessments do not need to be repeated at this timepoint, but if there are any incidental findings between screening assessments and this timepoint that would make the patient ineligible, they will be excluded from moving forward with LD/cell infusion
  - No disease complications from bridging therapy or related to the patient's underlying disease that, in the opinion of the investigator, would make it unsafe to proceed with LD chemotherapy or TCR infusion.
  - Adequate respiratory function with oxygen saturation  $\geq 94\%$  on room air and no dyspnea at rest.
  - No new cardiac issues, including CHF, MI, arrhythmias, or stroke.
  - No evidence of an active infection (e.g., temperature  $\geq 38.3^{\circ}\text{C}$ , positive blood cultures, requirement for antibiotics) within 14 days before LD chemotherapy.

#### **10.5 Evaluations prior to T cell infusion**

On the day of scheduled T cell infusion, the patient should undergo a clinical evaluation and a clinical determination for appropriateness to proceed with treatment.

- 1) Interval history and physical exam and ECOG performance status
- 2) Blood draw for laboratory studies:
  - a. CBC, differential, platelet count
  - b. Renal/Hepatic Function Panel
  - c. Magnesium and Lactate Dehydrogenase (LDH)
  - d. Uric acid
- 3) Serum pregnancy test within 72 hours of infusion

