### APPENDIX A: Schedule of Evaluations

Assessment	Screening	Pretreatment Evaluation	Lymphodepleting Chemotherapy (Day -4 to -2)	T cell Infusion (Day 0)							*see Note
					1	3	7	14	21	28	
Window		-30 days of leuka		Up to 7 days post-LD chemo	+/- 1 d	+/- 1 d	+/- 1 d	+/- 3 d	+/- 3 d	+/- 3 d	Day 60 +/- 14 days, Day 90-365 +/- 30 days
Informed consent/HIPAA	X	X									
HLA typing	X a										
MAGE A1 evaluation	X										
I/E criteria		X									
Medical history a	X				X		X	X	X	X	
Physical exam	X	X	X	X		X	X	X	X	X	
Height/weight b	X		X								
ECOG performance status	X	X	X								
Pregnancy test	X			X b							
Vitals including O 2 sat				X c							
Brain imaging b	X										
12-lead ECG	X										
MUGA/ECHO d		X									

RG1007463  
IR10420

Assessment	Screening	Pretreatment Evaluation	Lymphodepleting Chemotherapy (Day -4 to -2)	T cell Infusion (Day 0)	*see Note						
					1	3	7	14	21	28	
Window	-30 days of leuka		Up to 7 days post-LD chemo		+/- 1 d	+/- 1 d	+/- 1 d	+/- 3 d	+/- 3 d	+/- 3 d	
											Day 60 +/- 14 days, Day 90-365 +/- 30 days
CT/PET scan i		X									Performed at the following timepoints if clinically indicated or suspicion of progression: 
 
• Approximately 1 month after each T cell infusion
 
• Approximately 3 months after each T cell infusion
 
• Approximately 6 months after the last T cell infusion
 
• Approximately 9 months after the last T cell infusion
 
• Approximately 12 months after the last T cell infusion
 
 Before the patient receives additional antitumor therapy
Tumor biopsy (in subjects with accessible disease)		X						X			Performed at week 12 after each infusion then as clinically indicated.,
Leukapheresis		X									
Lymphodepleting chemotherapy			X								
T cell admin				X							
AEs		X	X	X	X	X	X	X	X	X	X
Neurological exam		X									

RG1007463  
IR10420

Assessment	Screening	Pretreatment Evaluation	Lymphodepleting Chemotherapy (Day -4 to -2)	T cell Infusion (Day 0)	*see Note							
					1	3	7	14	21	28		
Window	-30 days of leuka		Up to 7 days post-LD chemo	+/- 1 d	+/- 1 d	+/- 1 d	+/- 3 d	+/- 3 d	+/- 3 d			Day 60 +/- 14 days, Day 90-365 +/- 30 days
CBC, differential, platelet count	X	X	X	X	X	X	X	X	X	X		Concurrent with restaging as clinically indicated Concurrent with T-cell persistence evaluation

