Renal, hepatic function with LDH, Mg	X	X	X	X	X	X	X	X	X	X		Concurrent with restaging as clinically indicated
Uric acid	X		X	X	X	X						
Serum ferritin	X											As clinically indicated
CRP	X											As clinically indicated
IL-6	X											As clinically indicated
DIC panel without platelets	X											As clinically indicated
Quantitative IgG f	X											Approximately monthly
Virology panel	X											
ABO blood typing; antibody screen	X											
G6PD screening	X											
T cell persistence	X	X			X	X	X	X	X	X		Approx. 6 weeks and 2, 3, 6, 9, and 12 months after the T cell infusion and at the time of tumor relapse
T cell cellular immune response		X								X		Approx 2, 3, 6, 9 and 12 months after the T cell infusion

RG1007463  
IR10420

Assessment	Screening	Pretreatment Evaluation	Lymphodepleting Chemotherapy (Day -4 to -2)	T cell Infusion (Day 0)	*see Note							
					1	3	7	14	21	28		
Window	-30 days of leuka		Up to 7 days post-LD chemo		+/- 1 d	+/- 1 d	+/- 1 d	+/- 3 d	+/- 3 d	+/- 3 d		
												Day 60 +/- 14 days, Day 90-365 +/- 30 days
RCL testing by VSVG qPCR	X											Approximately 3, 6, and 12 months after the last T cell infusion
Serum archive	X	X			X	X	X	X	X	X		Approximately at 3, 6, 9 and 12 months after the last T cell infusion
Citrate plasma archive	X	X			X	X	X	X	X	X		Approximately at 3, 6, 9 and 12 months after the last T cell infusion
Tumor Biopsy	X							X				Prior to enrollment, 2 weeks after and 12 weeks after the first T cell infusion.

\*NOTE: Protocol time points represent guidelines for performance of required evaluations. Due to numerous factors influencing scheduling (subject and provider availability, testing services limitations, etc.), variation in evaluation performance dates is anticipated and acceptable to the protocol (i.e., within  $\pm$  4 days of time points < day 30;  $\pm$  30 days for timepoints > day 30). Evaluations do not need to be repeated if results from previous test are available and within protocol window

a Medical history to include hematologic, cytogenetic, flow cytometric, and histologic findings at diagnosis and time of enrollment as well as prior therapies and response to therapy.

b Height required only at Pretreatment Evaluation.

c Vital signs and O2 saturation being recorded before, approximately **every 15 minutes during**, at completion of the infusion, and hourly after the infusion for at least 2 hours after infusion.

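### The text reviewed requires no pregnancy test just before lymphodepletion; the only test after screening is timed to infusion, and its window opens after lymphodepletion has begun

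*Combined protocol and SAP*

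**What the plan says.** Appendix A marks a pregnancy test at screening and another at the T cell infusion. Section 10.5 times the second one as a "Serum pregnancy test within 72 hours of infusion", and an Appendix A footnote repeats the rule: "Pregnancy test within 72 hours of cell infusion". Both are tied to the infusion, not to LD.

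Section 10.4 is the checkpoint before LD, within 5 days of its start. It lists an interval history, physical examination, ECOG status, blood count, renal and hepatic panel, magnesium, LDH and research blood. No pregnancy test is listed. Patients must "Continue to meet all inclusion/exclusion criteria", but the section adds that "All assessments do not need to be repeated at this timepoint" and bars a patient from LD on the strength of incidental findings.

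Appendix A puts LD on Day -4 to Day -2, with infusion on Day 0 or "Up to 7 days post-LD chemo". It does not say whether the 7 days run from the first or the last LD dose. Its note on time points says that "variation in evaluation performance dates is anticipated and acceptable to the protocol", giving 4 days either side for time points before day 30 and 30 days after that. It also says: "Evaluations do not need to be repeated if results from previous test are available and within protocol window".

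Section 10.8 makes pregnancy a reason to stop active treatment and foresees a second LD course.

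**The concern.** LD is the first treatment that the protocol gives in each course that includes it, yet the pregnancy check is tied to the step that follows. A site working from sections 10.4 and 10.5 as written could start LD on the screening result plus a history and examination, neither of which is a test for early pregnancy. A new pregnancy would then come to light at the infusion check. By that point the patient has had lymphodepleting chemotherapy, and under section 10.8 she can no longer receive the cells it was meant to support.

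The plan is stricter with other time-sensitive items. Section 10.4 rechecks oxygen saturation, new cardiac problems and recent infection. Imaging must be repeated if it is more than 45 days old at first infusion (pretreatment evaluations, item 7), and within 30 days before a second LD course (section 10.7). The text reviewed sets no age limit at LD for the pregnancy result, although bridging chemotherapy may be given between enrollment and LD.

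**Working it through.** The plan gives no figure to reproduce, so the check is day arithmetic plus a comparison of the lists.

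**Inputs.** The test window is 72 hours before infusion (section 10.5). LD is Day -4 to Day -2, taken as three consecutive days, and infusion may follow up to 7 days after LD (Appendix A). The pre-LD evaluation is within 5 days before LD (section 10.4). The 12-week evaluation is taken as Day 84, with 7 days either side (section 10.7) or 30 days either side (Appendix A note).

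**When the window opens.** 72 hours is 3 days, so it opens on Day 0 - 3 = Day -3. The delay after the first LD dose is -3 minus the day of that dose.

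| First LD day | Last LD day | Window opens after first dose | LD days before window | Permitted if the 7 days run from |
|---|---|---|---|---|
| -4 (nominal) | -2 | 1 day | 1 of 3 | either dose |
| -5 | -3 | 2 days | 2 of 3 | either dose |
| -6 | -4 | 3 days | 3 of 3 | either dose |
| -7 | -5 | 4 days | 3 of 3 | either dose (limit if first) |
| -8 | -6 | 5 days | 3 of 3 | last dose only |
| -9 | -7 | 6 days | 3 of 3 | last dose only (limit) |

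**Effect of the 4-day tolerance.** There are two ways to apply it.
- Added to the 72 hours, it reaches Day -3 - 4 = Day -7. That is on or before the first dose in the first four rows (the same day when LD starts on Day -7), and 1 or 2 days too late in the last two.
- Applied to Day 0, it reaches Day -4. That meets the first dose only on the nominal schedule, and only on the same day.

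Either way the tolerance allows an earlier test without requiring one.

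**Age of the result at LD, first course.** The result on file dates from screening, before leukapheresis. The text reviewed does not give the time from leukapheresis to LD, so the age cannot be calculated.

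**Age of the result, second course with LD.** The last scheduled test falls on Day -3 to Day 0 of the first infusion. At Day 84 it is 84 to 84 + 3 = 87 days old. The youngest it can be at that evaluation is 84 - 7 = 77 days under section 10.7, or 84 - 30 = 54 days under the Appendix A tolerance. If second LD starts after the evaluation, the result is older still.

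**Could a pre-LD test replace the 72-hour test?** A test taken 5 days before LD would, at infusion, be:
- 5 + 4 = 9 days old on the nominal schedule;
- 5 + 7 = 12 days old at the limit counted from the first dose;
- 5 + 2 + 7 = 14 days old at the limit counted from the last dose.

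The current rule allows 3 days, so both tests are needed.

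**The case against.** The strongest objection is that this argues from absence. The text reviewed begins partway through the pretreatment list and lacks the eligibility criteria, the LD administration section and the second-infusion rules. A pre-LD pregnancy rule could well sit in one of them. Section 10.4 makes continued eligibility binding, and its waiver of blanket repetition would not override a timed test in the criteria. This stands as a limit on the conclusion. On the visible wording, however, continued eligibility is policed through incidental findings, and no listed evaluation would reveal an early pregnancy.

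Appendix A also appears to place early evaluations within 30 days of leukapheresis, and earlier results may stand only inside the protocol window. Both points are fair, and a result of any age is not acceptable for entry. Neither limits the age of the result at LD.

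The position of the first test in the extracted table is uncertain; it might belong under pretreatment rather than screening. The lists in sections 10.4 and 10.5 show the gap without the table.

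Finally, the group at risk is small, LD is conditional, and the longer delays depend on how the 7-day limit is read. All true. The nominal schedule alone still puts the first LD dose before the window opens, and where no LD is given the 72-hour test is adequate.

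**Conclusion.** The concern holds on the text reviewed. No pregnancy test is required between screening and the first LD dose, or between the test before the first infusion and a second LD course. On the nominal schedule the only later window opens 1 day after LD begins, with 1 of 3 LD days already given. At the longest permitted gap it opens 4 or 6 days after LD begins, with all 3 given.

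This rests on three assumptions: LD runs on three consecutive days; a second course follows the 12-week evaluation; and the sections not available add no pre-LD test. The last matters most and keeps confidence moderate. Those affected are LD recipients of childbearing potential, a subset of the planned 15 to 18 patients whose size the documents do not give. The issue is avoidable exposure of a pregnant patient, with no claimed effect on power or error rates.

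**What to change.** Add a serum pregnancy test for patients of childbearing potential to the section 10.4 evaluations, for every course that includes LD, with the result available before the first LD dose. Mark it in the pregnancy row of Appendix A. The result would then be at most 5 days old when LD starts. Keep the 72-hour pre-infusion test.

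If the eligibility, LD administration or second-infusion sections already require a pre-LD test, it is enough to bring section 10.4 and Appendix A into line with them.

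The cost is one line and one table mark in the protocol, plus one extra laboratory result per patient of childbearing potential per LD course. The sample can come from the blood draw already scheduled in section 10.4. The drawback is that LD must wait for the result.
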